13.4. FINAL REPORT

Whether the study is completed or prematurely terminated, the Sponsor will ensure that the clinical study report is prepared and provided to the regulatory agency(ies) as required by the applicable regulatory requirement(s). The Sponsor will also ensure that the clinical study reports in marketing applications meet the standards of the ICH harmonised tripartite guideline E3: Structure and content of clinical study reports.

Where required by applicable regulatory requirements, an Investigator signatory will be identified for the approval of the clinical study reports. The Investigator will be provided reasonable access to statistical tables, figures, and relevant reports and will have the opportunity to review the complete study results.

Upon completion of the clinical study reports, the Sponsor will provide the Investigator with the full summary of the study results. The Investigator is encouraged to share the summary results with the study patients, as appropriate. The study results will be posted on publicly available clinical trial registers.

Irrespective of the outcome of the clinical trial, the Sponsor shall submit a summary of the results of the clinical trial to the EU database within 1 year from the end of the trial in all Member States concerned.

APPENDIX 1. SCHEDULES OF ASSESSMENTS

Table 7: Part A: Placebo-Controlled Treatment Period Schedule of Assessments

Event/Assessment	Screening	Baseline	Week 4	Week 12	Week 24	Week 36	Week 48	ET Visit ^a	Safety F/U █ after last dose of study drug ^b	Safety F/U Phone Screen █ after last dose of study drug ^b
Visit Number	0	1	2	3	4	5	6	-	Variable ^c	Variable ^c
Study Day	█	1	28	84	168	252	336	-	343	373
Visit Window (days) ^d	N/A	±7	±7	±7	±7	±7	±7		±3	±5
Clinic visit	X	X	X	X	X	X	X	X	X	
ICF	X									
Inclusion/ exclusion	X	X								
Demographics	X									
Medical history	X									
Weight ^e	X	X			X		X	X	X	
Height ^e and BMI	X									
Genetic confirmation of FSHD ^f	X									
Randomization		X								
█	█									
Urine drug screen ^h	X									
Vital signs ⁱ	X	X	X	X	X	X	X	X	X	
Standard 12-lead ECG ^j	X	X	X	X	X	X	X	X	X	
Physical examination ^k	X	X	X	X	X	X	X	X	X	
Urinalysis	X	X	X	X	X	X	X	X	X	
Serum FSH ^l	X									
Serum pregnancy test ^m	X									

Event/Assessment	Screening	Baseline	Week 4	Week 12	Week 24	Week 36	Week 48	ET Visit ^a	Safety F/U [REDACTED] after last dose of study drug ^b	Safety F/U Phone Screen [REDACTED] after last dose of study drug ^b
Visit Number	0	1	2	3	4	5	6	-	Variable ^c	Variable ^c
Study Day	[REDACTED]	1	28	84	168	252	336	-	343	373
Visit Window (days) ^d	N/A	±7	±7	±7	±7	±7	±7		±3	±5
Urine pregnancy test ⁿ		X	X	X	X	X	X	X	X	
Hematology	X	X	X	X	X	X	X	X	X	
Serum chemistry ^o	X	X	X	X	X	X	X	X	X	
Serology (HBsAg, HCV, and HIV 1/HIV 2) ^p	X									
PK ^q			X					X	X ^r	
[REDACTED]		[REDACTED]	[REDACTED]					[REDACTED]	[REDACTED]	
RWS	X	X	X	X	X	X	X	X ^r		
Hand-Held Dynamometry		X	X	X	X	X	X	X ^r		
Neuro-QoL UE Function	X	X	X	X	X	X	X	X ^r		
MSK MRI	X				X		X	X ^r		
PGIC			X	X	X	X	X	X ^r		
[REDACTED]			[REDACTED]	[REDACTED]	[REDACTED]	[REDACTED]	[REDACTED]	[REDACTED]	[REDACTED]	
[REDACTED]		[REDACTED]	[REDACTED]							
[REDACTED]		[REDACTED]	[REDACTED]							
[REDACTED]		[REDACTED]			[REDACTED]		[REDACTED]	[REDACTED]	[REDACTED]	
[REDACTED]		[REDACTED]			[REDACTED]		[REDACTED]	[REDACTED]	[REDACTED]	
[REDACTED]		[REDACTED]			[REDACTED]		[REDACTED]	[REDACTED]	[REDACTED]	
[REDACTED]		[REDACTED]			[REDACTED]		[REDACTED]	[REDACTED]	[REDACTED]	
Study drug dispensation		X	X	X	X	X	X			

Event/Assessment	Screening	Baseline	Week 4	Week 12	Week 24	Week 36	Week 48	ET Visit ^a	Safety F/U [REDACTED] after last dose of study drug ^b	Safety F/U Phone Screen [REDACTED] after last dose of study drug ^b
Visit Number	0	1	2	3	4	5	6	-	Variable ^c	Variable ^c
Study Day	[REDACTED]	1	28	84	168	252	336	-	343	373
Visit Window (days) ^d	N/A	±7	±7	±7	±7	±7	±7		±3	±5
Study drug count			X	X	X	X	X	X		
Qualitative exit interview								X		
Medications review	Continuous from signing ICF through [REDACTED] safety follow-up visit									
Concomitant treatments and procedures										
Adverse events										

Abbreviations: BMI = body mass index; ECG = electrocardiogram; [REDACTED] ET = early termination; FSH = follicle stimulating hormone; FSHD = facioscapulohumeral muscular dystrophy; F/U = follow-up; HBsAg = hepatitis B surface antigen; HCV = hepatitis C virus; HIV = human immunodeficiency virus; ICF = informed consent form; MRI = magnetic resonance imaging; MSK = musculoskeletal; Neuro-QoL = Quality of Life in Neurological Disorders; [REDACTED]; PGIC = Patient Global Impression of Change; [REDACTED]; PK = pharmacokinetics; PRO = patient-reported outcome; RWS = reachable workspace; UE = upper extremity.

^a If a patient prematurely discontinues study treatment, they will be encouraged to remain in the study and continue with all other aspects of the study. If a patient decides to prematurely discontinue study treatment and not continue with all other aspects of the study, they will be considered to have withdrawn from the study. If a patient withdraws from the study, they will be asked to complete an ET visit as soon as possible after the decision to terminate study participation and to complete the safety follow-up visit [REDACTED] days and a safety phone screen [REDACTED] days after their last dose of study drug. If the ET visit will be scheduled more than [REDACTED] after the last dose of study drug, the safety follow-up and ET visits may be combined, with no duplication of assessments required.

^b The [REDACTED] and [REDACTED] safety follow-up visits will be required for all patients who discontinue study treatment early or do not to rollover into Part B. The [REDACTED] safety follow-up visit may be performed as a phone screen, unless ongoing clinical laboratory findings or AEs require additional follow-up.

^c Patients who do not rollover into Part B only.

^d Scheduled visits may be split over 2 days, if required, and must be completed within the protocol-defined visit windows. Unscheduled visits may be performed if clinically indicated.

^e Weight and height will be measured with shoes off and preferably with the same balance at each visit.

^f Genetic confirmation must be obtained before the patient is randomized. Genetic confirmation can come from previous testing, if verified with appropriate documentation from an accredited laboratory. If genetic testing is necessary, the [REDACTED] screening window and activities will not start until the results are obtained and verified by the Principal Investigator.

^g Patients must have a Ricci score of 2 to 4 to be eligible. The score will be assigned according to the worst clinical assessment on physical examination. Patients who are wheelchair-dependent or dependent on walker or wheelchair for activities are not permitted to enroll in the study.

- ^h Urine drug screen is for drugs of abuse including cocaine, amphetamines, opiates (morphine), benzodiazepines, and cannabinoids.
- ⁱ Vital signs (pulse rate, respiration rate, blood pressure, and temperature) will be collected after the patient has been seated or recumbent for at least 5 minutes and before any 12-lead ECG assessment or blood sampling is performed.
- ^j Twelve-lead ECGs will be performed after patients have been recumbent for at least 5 minutes, after the measurement of vital signs, and before any procedures that may affect heart rate (eg, blood sampling).
- ^k Physical examination at the screening visit and safety follow-up includes an evaluation of body systems, including but not limited to the following: skin; head, eyes, ears, nose, and throat; respiratory system; cardiovascular system; abdomen (liver, spleen); lymph nodes; neurological system; and musculoskeletal system.
- ^l Serum follicle-stimulating hormone testing is required for suspected postmenopausal female patients only.
- ^m Serum pregnancy tests will be performed for all female patients of child-bearing potential at the screening visit.
- ⁿ Urine pregnancy tests will be performed for all female patients of child-bearing potential before randomization and before dispensation of study drug at all other visits. If pregnancy is found, patients must be terminated from the study effective immediately. Home pregnancy tests will be performed for all female subjects of child-bearing potential if required per local regulations.
- ^o For the screening visit, patients will be required to fast for at least 4 hours prior to laboratory blood samples being taken.
- ^p Subjects with a known history of hepatitis infection must be tested to confirm active infection. All subjects will be tested for hepatitis B surface antigen and, if positive, will not be allowed to enroll in the study. All subjects will be tested for hepatitis C antibody and, if positive, should be tested for viral RNA. If the viral RNA test is negative indicating inactive/resolved hepatitis C infection, then the subject can enroll in the study as long as their liver panel is within range of the inclusion and exclusion criteria ([Section 4.1](#)). If the viral RNA test is positive, indicating active viral hepatitis C, the subject will not be allowed to enroll in the study. **For Italy only:** Tuberculosis will also be tested at Screening ([Appendix 2](#)).
- ^q Patients will be required to take their study drug dose in-clinic and blood collection for PK will occur immediately predose and 4 hours (± 30 minutes) after administration of the study dose.
- ^r If the ET visit occurs ≥ 12 weeks after the last visit, noted assessments should be performed. If the ET visit occurs ≥ 24 weeks after the last visit, MRI should be performed.

Table 8: Part B: Open-Label Extension Schedule of Assessments

Event/Assessment	Year 1				Year 2		Safety F/U █ after last dose	Safety F/U Phone Screen █ after last dose of study drug ^b
	Baseline ^a Week 48	Week █	Weeks █	Week █	Weeks █	Weeks █		
Visit number ^c	1	2	3, 4, 5	6	7+	8+	Variable	Variable
Visit window (days)	+7	+7	±14	±14	±14	±14	±3	±5
Clinic visit	X		X	X		X	X	
Phone call		X			X			X
ICF	X							
Inclusion/exclusion	X							
Weight ^d	X		X	X		X	X	
Height ^d and BMI	X							
Vital signs ^e	X		X	X		X	X	
Standard 12-lead ECG ^f	X			X		X ^g	X	
Physical examination ^h	X		X	X		X	X	
Urinalysis	X		X	X		X	X	
Urine pregnancy test ⁱ	X		X	X		X	X	
Hematology	X		X	X		X	X	
Serum chemistry ^j	X		X	X		X	X	
Study drug	X		X	X		X		

Event/Assessment	Year 1				Year 2		Safety F/U █ after last dose	Safety F/U Phone Screen █ after last dose of study drug ^b
	Baseline ^a Week 48	Week █	Weeks █	Week █	Weeks █	Weeks █		
Visit number ^c	1	2	3, 4, 5	6	7+	8+	Variable	Variable
Visit window (days)	+7	+7	±14	±14	±14	±14	±3	±5
Clinic visit	X		X	X		X	X	
Phone call		X			X			X
dispensation								
Study drug count			X	X		X		
Concomitant meds & procedures	Continuous from signing ICF through █ safety follow-up visit							
Adverse events								

Abbreviations: BMI = body mass index; ECG = electrocardiogram; █; FSHD = facioscapulohumeral muscular dystrophy; F/U = follow-up; ICF = informed consent form; PRO = patient-reported outcome; RWS = reachable workspace.

^a In most cases, the baseline visit of Part B will occur on the same day as Week 48 visit of Part A, and patients should complete all Part A Week 48 assessments before signing the informed consent for Part B. Informed consent for Part B will be signed before any Part B specific assessments are performed. In the event that a patient has their baseline visit of Part B after the Part A Week 48 visit (but within the █ window), they will NOT have to repeat any Part B assessments that were specified to be performed at the Week 48 visit of Part A.

^b The █ safety follow-up will be required for all patients who discontinue study treatment early. This assessment may be performed as a phone call, unless ongoing clinical laboratory findings or adverse events require additional follow-up.

^c Unscheduled visits may be performed if clinically indicated.

^d Weight and height will be measured with shoes off and preferably with the same balance at each visit.

^e Vital signs (pulse rate, respiration rate, blood pressure, and temperature) will be collected after the patient has been seated or recumbent for at least 5 minutes and before any 12-lead ECG assessment or blood sampling is performed.

^f Twelve-lead ECGs will be performed after patients have been recumbent for at least 5 minutes, after the measurement of vital signs, and before any procedures that may affect heart rate (eg, blood sampling).

^g Twelve-lead ECGs will be performed annually after █ (ie, only at █)

^h Physical examinations include an evaluation of body systems, including but not limited to the following: skin; head, eyes, ears, nose, and throat; respiratory system; cardiovascular system; abdomen (liver, spleen); lymph nodes; neurological system; and musculoskeletal system.

ⁱ Urine pregnancy tests will be performed for all female patients of childbearing potential before dispensation of study drug at all other visits. If pregnancy is found, patients must be terminated from the study effective immediately. Home pregnancy tests will be performed for all female subjects of child-bearing potential if required per local regulations.

^j For baseline visit, patients will be required to fast for at least 4 hours prior to laboratory blood samples being taken.

APPENDIX 2. COUNTRY/REGION-SPECIFIC DIFFERENCES

The full history of this protocol is detailed below, including all past and current global and country-specific amendments:

Protocol History	
Version and Date of Protocol	Comments
Version 1.0, 17 February 2022	Original version
Version 2.0, 03 March 2022	Global Amendment 1
Version 2.1, 27 July 2022	UK-specific amendment
Version 2.2, 21 September 2022	Germany-specific amendment
Version 2.3, 11 October 2022	Germany-specific amendment
Version 3.0, 08 August 2022	Global Amendment 2
Version 3.1, 12 October 2022	UK-specific amendment
Version 3.2, 17 November 2022	Germany-specific amendment
Version 3.3, 22 November 2022	Italy-specific amendment
Version 4.0, 01 March 2023	Global Amendment 3
Version 4.1, 22 March 2023	UK-specific amendment
Version 4.2, 22 March 2023	Italy-specific amendment
Version 5.1, 21 December 2023	Global Amendment 4 (current version)

Italy-specific differences:

Change and Rationale	Affected Sections
Added exclusion of vaccination with a live attenuated vaccine within 6 weeks prior to randomization until the safety follow-up visit	Section 4.1.1.2
Added tuberculosis to the serology testing at screening	Section 6.1.5, Table 7

APPENDIX 3. DRUGS POTENTIALLY AFFECTING MUSCLE FUNCTION

Potential list of drugs or supplements that may affect muscle function includes, but is not limited to, the following:

1. Statins
2. Steroids
3. Testosterone or other growth hormone agonists
4. Beta-agonists
5. Creatine
6. Colchicine
7. Benzylpenicillin

For patients who are on drug(s) or supplements that may affect muscle function, patients must be on a stable dose of that drug(s) or supplement for at least 3 months prior to the first dose of study drug and remain on that stable dose for the duration of the study. Changes to the dose or treatment discontinuation during the study can only be done for strict medical reasons by the treating physician with clear documentation and notification to the Sponsor.

Treatment with a statin can be initiated during the study if it is medically required. In this case, preference should be given to hydrophilic statins (e.g., pravastatin, rosuvastatin, fluvastatin) over lipophilic statins (e.g., simvastatin, atorvastatin, lovastatin.) Particular attention should be paid to creatine phosphokinase (already part of the laboratory safety monitoring) in patients who start treatment with a statin during the study.

APPENDIX 4. LIST OF OAT1/OAT3 SUBSTRATES WITH A NARROW THERAPEUTIC INDEX

Potential lists of drugs that are substrates of OAT1/OAT3 and have a narrow therapeutic index (NTI) are included below.

OAT1/OAT3 Substrates with NTI
valproic acid
clofarabine
methotrexate
mercaptopurine
baricitinib
pemetrexed

Source: <https://go.drugbank.com/categories/DBCAT003983>

FSHD2	Facioscapulohumeral muscular dystrophy type 2
GCP	Good Clinical Practice
ICH	International Council for Harmonization
ICF	Informed consent form
IDMC	Independent Data Monitoring Committee
LLOQ	Lower limit of quantification
LMV	Lean muscle volume
LME	Linear mixed-effects model
LS	Least squares
MedDRA	Medical Dictionary for Regulatory Activities

REACH TRIAL

MFF	Muscle fat fraction
MFI	Muscle fat infiltration
MI	Multiple imputation
MMRM	Mixed-effects model for repeated measures
MRI	Magnetic resonance imaging
Neuro-QoL	Quality of Life in Neurologic Disorders
Neuro-QoL-UE	Quality of Life in Neurologic Disorders – Upper Extremity
[REDACTED]	[REDACTED]
PD	Pharmacodynamic(s)
PFS	Physical Function Scale
PGIC	Patient Global Impression of Change
[REDACTED]	[REDACTED]
[REDACTED]	[REDACTED]
[REDACTED]	[REDACTED]
PK	Pharmacokinetic(s)
PR	ECG measurement
PRO	Patient-reported outcome
PT	Preferred term
Q	Quadrant
QoL	Quality of life
QT	ECG measurement
QTc	QT interval corrected
QTcF	QT interval corrected for heart rate by Fridericia's formula
RSA	Relative surface area
RWS	Reachable workspace
SAE	Serious adverse event
SAP	Statistical analysis plan
SD	Standard deviation
SE	Standard error
SOC	System Organ Class
SLS	Symptoms and Limitations Scale
TEAE	Treatment-emergent adverse event
UE	Upper extremity
ULN	Upper limit of normal
WB	Whole-body
WHO DD	World health organization drug dictionary

TRADEMARK INFORMATION

SAS®	SAS (Statistical Analysis Software) is a registered trademark of SAS Institute Inc.
------	-------------------------------------------------------------------------------------

REVISION HISTORY

Version	Date	Summary of revisions

1. INTRODUCTION

Facioscapulohumeral muscular dystrophy (FSHD) is a serious, rare, progressive, and debilitating neuromuscular disease, characterized by muscle weakness and eventual loss of muscle function. The progression of the disease significantly impacts activities of daily living (ADLs), independence, self-esteem, and mental status, with some patients experiencing pain and lost ability to function or work. No therapy has been proven to reduce disease severity or delay the progression of the disease; therefore, there is a high unmet need for an effective therapy for FSHD.

This study (REACH) is a Phase III double-blind, randomized, placebo-controlled trial of losmapimod, an orally bioavailable small molecule inhibitor of the p38 α / β mitogen-activated protein kinase (MAPK). The study is being conducted in 2 parts: a 48-week placebo-controlled treatment period (Part A) and an open-label extension (OLE, Part B) to allow patients to continue receiving losmapimod after completion of Part A. Prior Phase I and II studies have shown that losmapimod has potential to be a safe and effective therapeutic in slowing the progression of FSHD.

This Statistical Analysis Plan (SAP) provides details of the summaries and analyses to be performed to report the findings of Part A of the study. It should be read in conjunction with the Clinical Study Protocol (CSP); 1821-FSH-301, v5.1,21 December 2023. A separate SAP will be written to describe the planned analyses for Part B.

2. STUDY OBJECTIVES AND ENDPOINTS

2.1 STUDY OBJECTIVES

[figure not shown]
2.1.1 Primary objective

The primary objective of the study is to evaluate the efficacy of losmapimod for the treatment of FSHD on disease progression assessed by RWS quantification of total relative surface area (RSA) Q1-Q5 with 500 g wrist weight, averaged over both arms.

[figure not shown]
2.1.2 Secondary objectives

The secondary objectives are:

- To evaluate Patient Global Impression of Change (PGIC) relative to placebo.
- To evaluate efficacy of losmapimod to slow accumulation of fat in muscle-by-muscle fat infiltration (MFI) with whole-body (WB) musculoskeletal (MSK) magnetic resonance imaging (MRI) relative to placebo.
- To evaluate relative change from baseline in shoulder strength by hand-held quantitative dynamometry relative to placebo.
- To evaluate the change in Quality of Life in Neurological Disorders: Upper Extremities (Neuro-QoL-UE) relative to placebo.
- To assess safety and tolerability of losmapimod in patients with FSHD.

- To evaluate relative change from baseline in muscle strength by hand-held quantitative dynamometry, relative to placebo.

2.1.4 Safety objectives

These are included in the Secondary Objectives (see 2.1.2).

2.2 STUDY ESTIMANDS

2.2.1 Primary estimand

The estimand of the primary analysis is the mean difference in the change from baseline in average total RSA Q1-Q5 with 500 g wrist weight at Week 48 between treatment groups, where average is applied over both arms. This evaluation will be carried out on the Full Analysis Set (FAS) (as per the ICH E9 (R1) [1]), which will consist of all randomized patients with FSHD type 1 (FSHD1) and FSHD type 2 (FSHD2) who receive at least one dose of study drug in the placebo-controlled treatment period. All observed data will be included in the primary analysis, including data collected after intercurrent events (as described in ICH E9 (R1) Addendum 2017), i.e., treatment discontinuation or a change in concomitant use of FSHD symptomatic medication. The change from baseline in average total RSA Q1-Q5 with 500 g wrist weight will be summarized by treatment group at each post-baseline visit. A mixed-effects model for repeated measures (MMRM) will be used as the primary analysis to analyze change from baseline in average total RSA Q1-Q5 with 500 g wrist weight (see 8.3.1, 10.2.1.1).

2.3 STUDY ENDPOINTS

[figure not shown]
2.3.1 Primary endpoint

Change from baseline in average total RSA Q1-Q5 with 500 g wrist weight at Week 48, where average is applied over both arms.

2.3.2 Secondary endpoints

- PGIC at Week 48
- Change from baseline in WB longitudinal composite MFI in B muscles at Week 48
- Relative change from baseline in average shoulder abductor strength by hand-held quantitative dynamometry at Week 48
- Change from baseline in Neuro-QoL-UE at Week 48
- Safety and tolerability, based on the assessment of adverse events (AEs), clinical laboratory tests, electrocardiograms (ECGs), vital signs, and physical examinations

2.3.3 Exploratory endpoints

- Relative change from baseline in muscle strength by hand-held quantitative dynamometry at Week 48

Abbreviations: MFI = muscle fat infiltration; [REDACTED].

2.4 STATISTICAL HYPOTHESES

2.4.1 Primary hypotheses

The null hypothesis for the primary endpoint is that the mean change from baseline in average total RSA Q1-Q5 with 500 g wrist weight at Week 48, where average is applied over both arms, is the same for the 2 treatment groups.

The alternative hypothesis for the primary endpoint is that the mean change from baseline in average total RSA Q1-Q5 with 500 g wrist weight at Week 48, where average is applied over both arms, differs between the 2 treatment groups.

2.4.2 Multiple testing strategy

To control the overall type I error rate, the primary endpoint and secondary efficacy endpoints will be tested in sequence as follows:

1. The primary endpoint will be tested at 2-sided significance level $\alpha=0.05$.
2. If a statistically significant result is obtained for the primary endpoint (test 1), change from baseline in WB longitudinal composite MFI in B muscles at Week 48 and relative change from baseline in average shoulder abductor strength by hand-held quantitative dynamometry at Week 48 will be tested using the Bonferroni procedure, i.e., each will be tested at 2-sided $\alpha = 0.025$ (test 2).
 - If both tests are significant, a statistically significant result is obtained from test 2. The remaining significance level from test 2 = 0.05.
 - If only one of the 2 tests is significant, a statistically significant result is obtained from test 2. The remaining significance level from test 2 = 0.025.
 - If neither test is significant, a statistically significant result is not obtained from test 2.
3. If a statistically significant result is obtained from test 2, PGIC at Week 48 will be tested at the remaining significance level from test 2 (test 3).
4. If a statistically significant result is obtained from test 3, change from baseline in Neuro-QoL-UE at Week 48 will be tested at the remaining significance level from test 3, which is equal to the remaining significance level from test 2.

In recognition of the complexities of this rare disease and the novelty of this research field, in case the result of the primary analysis (MMRM) of the primary endpoint is on the boundary of statistical significance, but at least one of the following is true:

- results from most sensitivity analyses are nominally significant,
- result of PGIC at Week 48 is nominally significant,
- result of Change from baseline in WB longitudinal composite MFI in B muscles at Week 48 is nominally significant,

AND

- results from most of the remaining secondary and exploratory efficacy endpoints are directionally favorable to losmapimod,

the totality of evidence will be utilized to support the decision making.

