5. SAMPLE SIZE CONSIDERATIONS

The target population for this clinical trial is patients with FSHD1 and FSHD2. The clinical trial will reflect the current epidemiologic information about FSHD, with patients with FSHD1 making up approximately 95% of the study population and the other 5% being people living with FSHD2.

Assuming the within-group standard deviation (SD) of change is 0.08, a sample size of 210 patients with FSHD1 (105 patients per group) will be needed to provide at least 95% power with a 2-sided t-test at 0.05 significance level to detect a difference of 0.05 between losmapimod and placebo for the primary endpoint. An additional approximately 20 patients with FSHD2 will be recruited. The primary analysis will include patients with FSHD1 and FSHD2. Premature withdrawal and missing data are discussed in 9.1.

For the secondary efficacy endpoints of change from baseline in WB longitudinal composite MFI of B Muscles and PGIC at Week 48, assuming the within-group SDs are 0.72 and 1.0 respectively, a sample size of 210 patients with FSHD1 will provide at least 95% power with a 2-sided t-test at 0.025 significance level to detect a difference of 0.5 and 0.6 respectively between losmapimod and placebo.

For the secondary efficacy endpoint of relative change from baseline in average shoulder abductor strength at Week 48, assuming the within-group SD is 46, a sample size of 210 patients with FSHD1 will provide at least 75% power with a 2-sided Wilcoxon rank-sum test at 0.025 significance level to detect a difference of 20.2 between losmapimod and placebo.

In the above calculations, the assumed treatment differences and SDs are based on results from an ongoing Phase 2 study, Study FIS-002-2019 (ReDUX4). It is also assumed that 10% of the study population has missing Week 48 data. All power calculations were performed using the POWER Procedure of SAS[®] Version 9.4.

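### Free improvement: 0.025 of alpha can go unused after Neuro-QoL-UE in SAP 2.4.2, and could be returned to the test-2 endpoint that missed

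*SAP*

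**What the plan says.** SAP 2.4.2 sets a gated sequence:

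1. The primary endpoint is tested at two-sided 0.05.
2. If it is significant, MFI in B muscles and relative change in average shoulder abductor strength are each tested at 0.025 (test 2). If both succeed, 0.05 is carried forward. For a single success the SAP says: "If only one of the 2 tests is significant, a statistically significant result is obtained from test 2", and "The remaining significance level from test 2 = 0.025".
3. PGIC is tested at whatever level test 2 passes on.
4. If PGIC is significant, "change from baseline in Neuro-QoL-UE at Week 48 will be tested at the remaining significance level from test 3", which equals the level left from test 2.

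Nothing follows step 4. Protocol 9.1.6.4 lays down no alpha sequence for the secondary endpoints, so SAP 2.4.2 is the only text that governs this.

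SAP section 5 gives shoulder strength "at least 75% power with a 2-sided Wilcoxon rank-sum test at 0.025 significance level to detect a difference of 20.2 between losmapimod and placebo", "assuming the within-group SD is 46, a sample size of 210 patients with FSHD1", with 10% of Week 48 data missing. MFI and PGIC are each given at least 95% power at 0.025. Neither document states an effect, SD or power for Neuro-QoL-UE.

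**The concern.** Suppose MFI is significant at 0.025 and shoulder strength has a p-value between 0.025 and 0.05. MFI's 0.025 passes to PGIC and, if PGIC succeeds, to Neuro-QoL-UE. If that succeeds as well, the 0.025 has nowhere to go, although it could validly be added to the 0.025 that shoulder strength still holds. The trial would then have won its primary endpoint and three secondary endpoints, and could not formally claim the fourth.

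Shoulder strength is the endpoint most exposed, because it has the lowest power of those for which the SAP gives a figure. It was also moved from exploratory to secondary in the current protocol version and placed ahead of PGIC in the sequence, so the claim evidently matters to the sponsor.

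**Working it through.** **Inputs (SAP section 5).** 105 FSHD1 patients per group with 10% missing gives n = 105 × 0.9 = 94.5 per group. Difference/SD: primary 0.05/0.08, MFI 0.5/0.72, PGIC 0.6/1.0, shoulder strength 20.2/46. Critical values: 1.960 for two-sided 0.05 and 2.241 for two-sided 0.025.

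**Step 1: reproduce the stated power.** Normal approximation: power = Φ(δ − z), with δ = (difference/SD) × √(n/2) and √(94.5/2) = 6.874. For the Wilcoxon test, n is multiplied by 3/π (its efficiency under normality), giving 90.2 and √(90.2/2) = 6.717.

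| Endpoint | δ | Level | Power |
|---|---|---|---|
| Primary | 0.625 × 6.874 = 4.296 | 0.05 | 99.0% |
| MFI | 0.694 × 6.874 = 4.774 | 0.025 | 99.4% |
| PGIC | 0.600 × 6.874 = 4.124 | 0.025 | 97.0% |
| Shoulder strength | 0.439 × 6.717 = 2.950 | 0.025 | 76.1% |
| Shoulder strength | 2.950 | 0.05 | 83.9% |

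Other approximations for the Wilcoxon test, and direct simulation of it, give 74.9% to 75.4% at 0.025. The SAP's 75% is reproduced.

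**Step 2: is the added step valid?** Consider the first true null hypothesis to be rejected.

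- If the primary null is true, the gate limits the error to 0.05.
- If shoulder strength is a true null and MFI is not, and some later endpoint is also a true null, the first false rejection is either shoulder strength at 0.025 or the first true null in the chain PGIC, Neuro-QoL-UE at 0.025. The sum is at most 0.05. Shoulder strength reaches 0.05 only after every other endpoint has been rejected, so in this case an error has already been counted.
- If shoulder strength is the only true null, it is tested at no more than 0.05.
- If MFI and shoulder strength are both true nulls, the bound is 0.025 + 0.025. If MFI is a true null and shoulder strength is not, the argument is the same with the two exchanged.
- If neither is a true null, the first true null among PGIC and Neuro-QoL-UE is tested at no more than 0.05.

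This is a Bonferroni graph in which Neuro-QoL-UE returns its alpha to the test-2 pair. After MFI, PGIC and Neuro-QoL-UE are rejected, the level for shoulder strength is 0.025 + 0.025 = 0.05. No independence assumption is used. Simulation over all 31 null configurations at correlations 0, 0.5 and 0.9 (400,000 trials each) gave a maximum family-wise error of 0.0505 both with and without the added step. The simulation standard error is √(0.05 × 0.95/400,000) = 0.0003, so both agree with 0.05.

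**Step 3: size of the gain.** With independent endpoints and Neuro-QoL-UE power q at 0.025:

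gain = (0.839 − 0.761) × 0.990 × 0.994 × 0.970 × q ≈ 7.5 points × q

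This is 2.2 points at q = 0.3, 3.7 at q = 0.5 and 6.7 at q = 0.9. Simulating the full sequence (1,000,000 trials) gives the power for shoulder strength after the change, in percent, with the gain in points:

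| Neuro-QoL-UE power (assumed) | Correlation 0 | Correlation 0.3 | Correlation 0.6 |
|---|---|---|---|
| No added step | 75.25 | 75.56 | 75.90 |
| 30% | 77.50 (+2.25) | 77.13 (+1.57) | 76.68 (+0.78) |
| 50% | 79.00 (+3.75) | 78.55 (+2.99) | 77.94 (+2.04) |
| 90% | 82.00 (+6.75) | 81.93 (+6.37) | 82.21 (+6.31) |

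The first row includes the primary gate. Starting from 75% marginal power instead of 76% adds about 0.2 points or less to each gain. The ceiling is the distance between the two levels: 83.9 − 76.1 = 7.8 points, or 83.0 − 75.0 = 8.0 points from the lower start.

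For MFI, power moves from 98.5% to at most 98.7%, about 0.2 points.

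**The case against.** The strongest reply is that nothing here is broken. The sequence is unambiguous, it controls the type I error, and no rule requires a plan to spend all its alpha. The branch that benefits is narrow: the primary, MFI, PGIC and Neuro-QoL-UE must all be significant and shoulder strength must fall between 0.025 and 0.05. For Neuro-QoL-UE power of 30% to 90% and independent endpoints, that is about 2% to 7% of trials. SAP 10.2.2.3 reports the shoulder-strength estimate and its 95% confidence interval in any case, so only the formal claim is lost.

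The size is also uncertain. Zero correlation is the favourable case when Neuro-QoL-UE power is modest, and protocol 3.2.2 describes associations of reachable workspace with PGIC and with MFI. All the assumed effects come from one Phase 2 study. If every noncentrality were 70% of that assumed (an illustrative figure, not from the documents), the gain with independent endpoints would be about 0.9 to 3.6 points across nominal Neuro-QoL-UE powers of 30% to 90%.

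These points stand, and they limit the finding to an optional efficiency of uncertain size. The argument that it is merely a design choice does not stand, because the alternative has no counterpart cost: every existing test keeps its place and level, and no rejection can be lost.

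**Conclusion.** The point holds as a free improvement and not as an error. In one branch of SAP 2.4.2, 0.025 is left unused. Returning it keeps strong control at 0.05 and raises shoulder-strength power by about 1-2, 2-4 or 6-7 points at Neuro-QoL-UE power of 30%, 50% or 90% (correlation 0 to 0.6), and by no more than about 8.

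The figures rest on the SAP's Phase 2 effects and SDs, 10% missing data, 210 FSHD1 patients and an assumed Neuro-QoL-UE power. The roughly 20 FSHD2 patients would raise power both before and after the change.

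A reader might infer three stronger things that the documents do not support:

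- That the sequence mishandles the type I error. It does not.
- That shoulder-strength power would simply become 79-82%. With near-independent endpoints that range needs Neuro-QoL-UE power of roughly 50% to 90%, which the documents do not state.
- That MFI significant with shoulder strength between 0.025 and 0.05 is enough to recover the claim. PGIC and Neuro-QoL-UE must both be significant as well.

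**What to change.** Add a fifth step to SAP 2.4.2:

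> 5. If exactly one of the two endpoints in test 2 was significant, and the tests in steps 3 and 4 are both significant, the other test-2 endpoint is tested at two-sided 0.05.

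If section 5 is to quote the resulting power for shoulder strength, it should state the assumed Neuro-QoL-UE power and show a range. The existing figure at 0.025 can stay as the power without the added step.

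The cost is one sentence, with no change to sample size, assessments, analysis models or the order of testing. It has to be in place before unblinding. A shoulder-strength p-value between 0.025 and 0.05 could not credibly be claimed under a rule written afterwards.
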